APPENDIX 3. BIRTH OUTCOMES OF SPECIAL INTEREST

Outcome	Definition
Preterm birth	Birth at <37 weeks gestation
APGAR score	
Abnormal	< 7.0 after 5 minutes
Moderately abnormal	4-6 at 5 minutes
Low	0-3 at 5 minutes
Small for gestational age (SGA)	Birth weight <10 th percentile
Birth weight	
Low birth weight	1500-2499 g
Very low birth weight	<1500 g

APPENDIX 4. NEONATAL AND INFANT OUTCOMES OF SPECIAL INTEREST

Outcome	Definition
Neonatal outcomes*	
Major congenital abnormality	
 Any structural or chromosomal abnormality diagnosed either at birth or in the first 30 days of life; will be assessed on a case-by-case basis, through investigator/delegate review of medical/hospitalization records and agreement by the Advisory Committee
Neonatal intensive care unit admission	
 Admission during the birth hospitalization
Neonatal pneumonia	
 Diagnosis made during birth hospitalization or subsequent hospitalization if admission occurred within 3 days following discharge from birth hospitalization; based on clinician assessment as recorded in the medical record
Respiratory distress syndrome	
 Diagnosis made during birth hospitalization or subsequent hospitalization if admission occurred within 3 days following discharge from birth hospitalization; based on clinician assessment as recorded in the medical record
Transient tachypnea of the newborn	
 Diagnosis made during birth hospitalization or subsequent hospitalization if admission occurred within 3 days following discharge from birth hospitalization; based on clinician assessment as recorded in the medical record
Pulmonary hypertension	
 Diagnosis made during birth hospitalization or subsequent hospitalization if admission occurred within 3 days following discharge from birth hospitalization; based on clinician assessment as recorded in the medical record
Inpatient encephalopathy	
 Encephalopathy diagnosed during birth hospitalization; based on clinician assessment as recorded in the medical record
Neonatal seizures/convulsions	
 Diagnosis made during birth hospitalization or subsequent hospitalization if admission occurred within 3 days following discharge from birth hospitalization; based on clinician assessment as recorded in the medical record
Neonatal sepsis	
 Diagnosis made during birth hospitalization or subsequent hospitalization if admission occurred within 3 days following discharge from birth hospitalization; based on clinician assessment as recorded in the medical record
Long duration of birth hospitalization	
 Duration of birth hospitalization ≥ 4 days
Hospital readmission post-birth hospitalization	
 Hospitalization ≤ 30 days of discharge date of birth hospitalization
Neonatal death	
 Death occurring in the first 28 days of life

Infant outcomes [†]	
Congenital abnormality	
 Any structural or chromosomal abnormality diagnosed between days 29 and 365 post-birth; will be assessed on a case-by-case basis, through evaluator review and agreement by the Advisory Committee
Hospitalized dengue	
 Acute febrile illness with a diagnosis of dengue (suspected or confirmed) requiring hospital admission
Death	
 Death occurring between days 29 and 365 post-birth

* Occurring or diagnosed in the first 28 days of life.

† Occurring or diagnosed between days 29 and 365 post-birth.

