- **Pregnancy related events:** will be defined as study AESIs (see Appendix 2) and other reported adverse events (serious and non-serious) occurring during the pregnancy, labour and delivery, or the puerperium. Pregnancy related AEs will be classified as: (i) pregnancy outcomes, (ii) complications of pregnancy, and (iii) complications of labour, delivery and puerperium. These outcomes were chosen based on their frequent presentation, their importance as markers of maternal and/or infant health, and their public health relevance. In addition, chorioamnionitis and hypertensive disorders of pregnancy are major risk factors for preterm birth. The definitions used for these outcomes will be consistent with local clinical practice, the European Medicine Agency (EMA) and United States Federal Drug Agency (US FDA) pregnancy guidance documents, and other published pregnancy outcome classification systems such as the European Surveillance of Congenital Anomalies (EUROCAT).
- **Birth outcomes:** will be defined as study AESIs and other reported adverse events (serious and non-serious) observed or diagnosed at birth. See Appendix 3 for the list of birth outcomes of special interest and their definition.
- **Neonatal and infant events:** Neonatal events will be defined as study AESIs and other reported adverse events (serious and non-serious) occurring between the day of birth (DOB) and 28 days post-DOB. Study AESIs and other reported adverse events (serious and non-serious) occurring between day 29 and 365 post-birth will be classified as infant events. See Appendix 4 for the list of neonatal and infant events of special interest and their definition.

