9.9 STRENGTHS AND LIMITATIONS OF THE RESEARCH METHODS

The most important strength of this study is that, unlike most pregnancy registries that rely on passive reporting, the identification and enrollment of pregnancy exposures will be active. Another important strength is that self-reported vaccination status and outcomes will be verified using medical record review and database linkages; thereby mitigating the risk of recall and reporting bias, a potential danger with retrospectively collected outcomes. Also, offsprings will be followed for up to 12 months post-birth to assess the risk of birth defects that may not be detected at birth, and to assess the risk of hospitalized and/or severe dengue among infants exposed in utero. On the other hand, this study will also have some limitations that need to be considered. First, the baseline dengue serostatus of most exposed pregnant women will not be known as the vaccinations studied occurred before the recent "test and vaccinate" recommendation. As such, should a safety concern arise, it will not be possible to distinguish between vaccine associated dengue in seronegative vaccinees from vaccine failure or waning immunity in seropositive vaccinees. Second, the majority of outcomes will be ascertained retrospectively, thus increasing the risk of recall and detection bias. However, this risk will be, in part, mitigated by the identification of outcomes using multiple data sources, and by the use of a sensitivity analysis stratified according to the nature of the outcomes (i.e., prospective vs. retrospective) if a sufficient number of women can be prospectively enrolled. Third, women who are unreachable, refuse to participate or have died prior to enrollment may be systematically different from study participants and thus, could introduce bias. However, permission will be sought from the Ethics Committee to obtain *aggregate* level information to undertake a comparison of participants and non-participants with regards to baseline characteristics and characteristics of prenatal care to assess the likelihood, strength and direction of such bias. Fourth, although the identification of CYD-TDV exposed pregnant women will be active, the database used to identify these women (SI-PNI EAPV) is part of Brazil's passive AEFI reporting system. As such, some pregnancy exposures may be missed despite educational efforts to stimulate reporting; however, there is no reason to believe that pregnancy exposures captured in the database will be systematically different from those who may be missed. As such, this will impact the precision of the results but not their validity. Fifth, the use of multiple data sources for identifying outcomes may introduce some discordance; however, the impact of this on outcome misclassification will be minimized by choosing *a priori* a gold standard source for each event. Sixth, given the young age of most vaccinees in Paraná, it is possible that many of the pregnancy exposure will be in adolescents; an age group less likely to carry the pregnancy to

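### Appendix 4 times several neonatal and infant AESIs in ways that do not agree with the protocol's own birth-to-day-28 neonatal window

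*Protocol*

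**What the plan says.** Section 9.3.1 defines neonatal events, both the study AESIs and any other adverse events reported, as those "occurring between the day of birth (DOB) and 28 days post-DOB"; days 29 to 365 are infant events. The footnote to the neonatal heading in Appendix 4 repeats the limit: "Occurring or diagnosed in the first 28 days of life".

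The rows under that heading use several other clocks:

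- Pneumonia, respiratory distress syndrome, transient tachypnea, pulmonary hypertension, seizures and sepsis: "Diagnosis made during birth hospitalization or subsequent hospitalization if admission occurred within 3 days following discharge from birth hospitalization".
- Encephalopathy: diagnosis in the birth stay only.
- Readmission: "Hospitalization ≤ 30 days of discharge date of birth hospitalization".
- Major congenital abnormality: diagnosis at birth or up to day 30, while the infant congenital abnormality row starts at day 29.
- Neonatal death: "Death occurring in the first 28 days of life", which agrees with the footnote.

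The infant list (days 29-365) has three items: congenital abnormality, hospitalized dengue and death. Section 9.9 gives as one reason for following offspring to 12 months "to assess the risk of hospitalized and/or severe dengue among infants exposed in utero".

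Section 9.2.3 compares rates of study AESIs with pre-vaccine background rates to find signals worth further investigation.

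**The concern.** One heading promises outcomes over a fixed age range, but the rows beneath it start and stop by date of discharge. For a baby who goes home early, the diagnosis-specific definitions close within days. A sepsis, pneumonia or seizure admission later in the first four weeks then enters no diagnosis-specific AESI row, since the infant list has none for these conditions. The exposure time behind each rate also varies with length of stay, which is itself related to the baby's health.

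What is at stake is the comparison in section 9.2.3. A registry rate that captures a few days, set against a background rate covering 28 days, would be too low and would lean towards missing a signal. With 214 reported exposures at most to date (section 9.5), a few events counted differently could matter.

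**Working it through.** The protocol gives no figure for how much of the neonatal window these definitions cover, so there is none to reproduce. The check is a day count.

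**Inputs**
- Neonatal window: 28 days after birth (section 9.3.1; Appendix 4 footnote).
- Latest qualifying admission: 3 days after discharge (Appendix 4).
- Length of an ordinary birth stay: not given. Appendix 4 treats "Duration of birth hospitalization ≥ 4 days" as a long-stay outcome, so stays of 1 to 3 days are assumed as ordinary and longer ones shown for range.

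**Six rows with the 3-day rule**

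Last qualifying admission day = stay + 3. Share of window excluded = (28 − min(28, stay + 3)) / 28.

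| Stay (days) | Last qualifying admission | Days excluded | Share |
|---|---|---|---|
| 1 | day 4 | 24 of 28 | 85.7% |
| 2 | day 5 | 23 of 28 | 82.1% |
| 3 | day 6 | 22 of 28 | 78.6% |
| 4 | day 7 | 21 of 28 | 75.0% |
| 7 | day 10 | 18 of 28 | 64.3% |
| 11 | day 14 | 14 of 28 | 50.0% |
| 25 | day 28 | 0 of 28 | 0% |

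More than half the window is excluded for any stay under 11 days. These are shares of days, not of events; the protocol gives no distribution of event timing.

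**Encephalopathy**

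With no allowance after discharge, the excluded share is (28 − stay) / 28. Stays of 1, 2 and 3 days give 27, 26 and 25 of 28 days (96.4%, 92.9%, 89.3%).

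**Readmission**

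Last qualifying day = discharge day + 30. Discharge on day 0 gives day 30; on day 2, day 32; on day 60, day 90. For every baby the row's limit lies beyond the footnote's day 28.

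**Congenital abnormality**

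The neonatal row ends on day 30 and the infant row begins on day 29. A diagnosis on day 29 or 30 fits both rows, and the neonatal row then breaches its own footnote.

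**Hospitalized dengue**

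The named AESI runs from day 29 to day 365. An admission on days 0-28 is outside it, although section 9.9 names infant dengue after in-utero exposure as a purpose of follow-up and sets no lower age limit.

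**The case against.** A reader might infer that most of the neonatal period goes unobserved, or that a sepsis admission on day 10 or a dengue admission on day 20 is not counted at all. The documents do not support that. Section 9.3.1 makes neonatal primary endpoints of the AESIs together with "other reported adverse events (serious and non-serious) occurring between the day of birth (DOB) and 28 days post-DOB". An admission after the birth stay can also meet the readmission AESI, section 11.1.1 always treats hospitalized dengue as serious, and offspring are followed to 12 months by interview and records. Only the diagnosis-specific label is lost.

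Nor is the 3-day rule, for an ordinary stay, a flat contradiction of the 28-day window. It is a narrower case definition inside that window, and both texts can hold. After a long stay the row alone would run past day 28 (a 35-day stay gives day 38), but reading row and footnote together cuts it off there. A late sepsis in a long-stay preterm baby is therefore an infant adverse event, not evidence that sick babies are observed for longer under these rows.

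The mismatch with background rates is also conditional. The protocol fixes no window for them, and its descriptions of SISPRENATAL, SINASC and SIM do not mention sepsis, pneumonia or seizures. A source restricted to the birth stay might match the present definitions. The abstract and section 9.7.1 speak of comparing rates of adverse events generally, so later events are not necessarily outside every comparison.

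All of this stands, and it limits the point to the AESI rates and their definitions. It does not reconcile the readmission row: if the footnote governs, the 30-day limit can never take effect; if the row governs, the footnote is wrong. It does not explain the two-day overlap for congenital abnormality or the day-29 start for dengue.

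**Conclusion.** The Appendix 4 windows need to be reconciled with section 9.3.1 and with their own footnotes. Under assumed stays of 1 to 3 days, the pneumonia, sepsis, seizure and pulmonary hypertension definitions exclude new admissions on 86% to 79% of the neonatal days, and encephalopathy excludes more. The resulting AESI rates are biased low if the background rate covers days 0-28, which is an assumption because the protocol does not say. The size of that bias cannot be worked out from the document.

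The readmission and congenital abnormality conflicts and the dengue gap follow from the text and need no assumption about stay. No data are lost and no precision figure in section 9.5 changes. This should be corrected because the inconsistency falls on the rates used to look for signals and is cheap to remove.

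**What to change.** In Appendix 4:

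- Define pneumonia, sepsis, seizures and encephalopathy by age: diagnosed on days 0-28, in the birth stay or any later admission. Alternatively, state the window of the background rate used for each and match it.
- Respiratory distress syndrome and transient tachypnea may keep the birth-stay rule. State which rule pulmonary hypertension follows.
- Move readmission out from under the 28-day footnote as a separately timed outcome.
- End the neonatal congenital abnormality row at day 28, so that the infant row follows at day 29 without overlap.
- Count hospitalized dengue from birth to day 365.

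The cost is revised wording and eCRF logic, with somewhat higher AESI rates than under the present rules. No new contacts are needed: the 0-3 month contact, the single retrospective interview and the review of hospitalization records already cover these dates (sections 9.4 and 9.6.1, Appendix 6).

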APPENDIX 5. BASELINE CHARACTERISTICS

Maternal baseline characteristics	Type of variable
Gestational age at CYD-TDV pregnancy exposure	Obtained from SI-PNI AEPV database
Mean (SD), weeks	
Median, weeks (25 th & 75 th percentile)	
Year of CYD-TDV pregnancy exposure	Derived from date of CYD-TDV pregnancy exposure
2016	
2017	
2018	
2019	
Socio-demographics	
Age at conception, years	Collected from questionnaire & verified using DOB and date of first CYD-TDV vaccination during pregnancy
Mean (SD), years	
Median (25 th & 75 th percentile), weeks	
1 st quartile	
2 nd quartile	
3 rd quartile	
4 th quartile	
BMI (at time of first CYD-TDV vaccination during pregnancy)	Derived from height, weight & age at cohort entry (first vaccination during pregnancy), and sex
<5 th percentile (underweight)	
5 th to <85 th percentile (normal)	
85 th to <90 th percentile (overweight)	
≥ 90 th percentile (obese)	
BMI (at time of first CYD-TDV vaccination during pregnancy)	Derived from height, weight & age at cohort entry (first vaccination during pregnancy), and sex
<18.5 (underweight)	
18.5 to <25 (normal)	
25 to <30 (overweight)	
≥30 (obese)	
Smoking status (at time of first CYD-TDV vaccination during pregnancy)	Collected from the questionnaire
Never smoker	
Past smoker	
Time since stopped	
Mean (SD), months/years	
Median (25 th & 75 th percentile), months/years	
Current smoker (during CYD-TDV exposed pregnancy)	
In the month before the pregnancy (yes/no)	
During the first trimester (yes/no)	
During the second trimester (yes/no)	
During the third trimester (yes/no)	
Alcohol consumption (during CYD-TDV exposed pregnancy)	Collected from the questionnaire
In the month before the pregnancy (yes/no)	
During the first trimester (yes/no)	
During the second trimester (yes/no)	
During the third trimester (yes/no)	
Highest level of education (at time of first CYD-TDV vaccination during pregnancy)	Collected from the questionnaire
None	
Primary school	

High school	
University/College	
Postgraduate	
Marital status (at time of first CYD-TDV vaccination during pregnancy)	Collected from the questionnaire
Single	
Married/Common law	
Divorced	
Widowed	
Household income (at time of CYD-TDV pregnancy exposure)	Collected from the questionnaire (minimum wage/month; SM equivalent ~ \$300 USD)
<1 SM	
1 to <3 SM	
≥3 to <5 SM	
≥5 to <10 SM	
≥ 10 SM	
Unknown/not reported	
Obstetrical and medical history (prior to first CYD-TDV vaccination during pregnancy)	
Gravidity	Collected from the questionnaire; total number of confirmed pregnancies regardless of the outcome
None	
1	
≥2	
Parity	Derived from Gravidity & question on number of pregnancies births Collected from the questionnaire; total number of births with >20 weeks gestation
None	
1	
≥2	
Previous miscarriage/spontaneous abortion (yes/no)	Collected from the questionnaire
Previous preterm birth (yes/no)	Collected from the questionnaire
Previous dengue infection	Collected from the questionnaire
Unknown	
Confirmed (describe method)	
Clinically diagnosed/unconfirmed	
Preexisting comorbidities (yes/no)	Collected from the questionnaire; confirmed using medical record review and/or health databases when available
Hypertension	
Diabetes	
Type I diabetes	
Type II diabetes	
Pulmonary disease (specific type)	
Heart disease (specify type)	
Renal disease (specify type)	
Vaccination and medication history	
Receipt of other vaccine(s) during pregnancy (specify)	Collected from the questionnaire, as well as from the “vaccination card” and/or “prenatal booklet” when available
Receipt of medications during pregnancy (specify)	Collected from the questionnaire; included prescription and non-prescription medications
Characteristics of prenatal care and delivery	
Gestational age at first prenatal visit, weeks	Derived from gestational age at first CYD-TDV vaccination

	during pregnancy & date of first prenatal visit; the latter should be available from either SISPRENATAL or the prenatal booklet
Number of prenatal care visits, mean (SD)	Collected from either SISPRENATAL or the prenatal booklet when available
Referral to specialist care (specify type of specialist)	Collected from the questionnaire and confirmed using SISPRENATAL or the prenatal booklet when available
Number of ultrasounds, mean (SD)	Collected (if data is available)
Index of prenatal care	Derived from number of prenatal care visits recorded in the prenatal booklet and/or SISPRENATAL when available
Adequate/plus (≥ 7 visits)	
Intermediate (3-6 visits)	
Inadequate (<3 visits)	
Hospitalization(s) during pregnancy	Collected from the questionnaire; confirmed using SISPRENATAL or the prenatal booklet or review of hospitalization records when available
Hospitalization <20 weeks gestation	
None	
1	
≥ 2	
Hospitalization ≥ 20 weeks gestation	
None	
1	
≥ 2	
Emergency Department (ED) visit(s) during pregnancy	Collected from the questionnaire; confirmed using SISPRENATAL or the prenatal booklet or review of hospitalization records when available
ED visit <20 weeks gestation	
None	
1	
≥ 2	
ED visit ≥ 20 weeks gestation	
None	
1	
≥ 2	
Method of delivery	Collected from questionnaire; confirmed using SINASC and/or birth hospitalization record if available
Vaginal	
Cesarean	
Planned	
Emergency	

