Participants' date of CYD-TDV immunization will be confirmed through probabilistic linkage (i.e., using nominal data) with the immunization registry; database linkages will be carried out by the DoH or study investigators depending on the availability of qualified personnel. When indicated, a women's self-reported exposure status will be reclassified using the immunization registry as the gold standard. In addition, reports of multiple CYD-TDV exposures during a pregnancy will be classified according to the earliest pregnancy exposure.

Women enrolled in the CYD-TDV pregnancy registry will be followed from the date of their first CYD-TDV vaccination during pregnancy (cohort entry) to up to 42 days following the end of the exposed pregnancy, regardless of the outcome of the pregnancy. The offspring of the exposed pregnancy will be followed for up to 12 months post-birth. In addition, women and offsprings enrolled prospectively (i.e., CYD-TDV exposure either soon before or after study start) will be followed until the earliest of: date of lost to follow-up, withdrawal of consent or death or end of study (July 2022).

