As the scenarios described above represent important threats to the validity of the results and to their generalizability, permission will be sought from the Ethics Committee to obtain *aggregate level* information (i.e., anonymized data) on rates of pregnancy, birth, neonatal and infant outcomes of special interest for non-participants, as well as *aggregate level* information on the baseline characteristics and characteristics of prenatal care of non-participants obtained from the MoH and DoH databases to enable a comparison of participants and non-participants, and assess the likelihood, strength and direction of the aforementioned biases. This comparison will also provide an assessment of the representativeness of the pregnancy registry participants.

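### Appendix 5 derives BMI from weight at vaccination in pregnancy with cut-offs that ignore gestational age, so pregnancy weight gain can be counted as overweight or obesity in the cohort description

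*Protocol*

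**What the plan says.** Appendix 5 of the protocol heads both BMI rows "BMI (at time of first CYD-TDV vaccination during pregnancy"), and gives the same derivation for each: "Derived from height, weight & age at cohort entry (first vaccination during pregnancy), and sex". One row uses percentile bands, with a category of "85 th to <90 th percentile (overweight"). The other uses fixed bands, with "25 to <30 (overweight") and obesity from 30 upwards. Neither row refers to gestational age.

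Section 9.2.2 ties cohort entry to vaccination: women are followed "from the date of their first CYD-TDV vaccination during pregnancy (cohort entry"). Under section 9.1.1 a qualifying vaccination may be given at any point in the pregnancy or in the 30 days before LMP. Neither section 9.3.2 nor Appendix 5 lists a pre-pregnancy weight or BMI.

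Section 8.2 makes the description of the exposed women secondary objective (i), and section 9.7.2 points to Appendix 5 for the variables.

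Appendix 5 also lists age at conception, with the source "Collected from questionnaire & verified using DOB and date of first CYD-TDV vaccination during pregnancy". LMP is among the data collected (section 9.3.2), and section 9.2.1 provides for an estimated conception date when LMP is not available.

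**The concern.** A baseline variable should mean the same thing for every woman in the table. This one is measured at a time that runs from before conception to near term. For a woman vaccinated around LMP it is in effect a pre-pregnancy BMI. For a woman vaccinated in the third trimester it includes the weight of the pregnancy, yet it is sorted by the same cut-offs.

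The stated rule can therefore classify a later-exposed woman as overweight or obese because she was pregnant when vaccinated. The shares of overweight and obese women are reported results under secondary objective (i), and the rule can only push them upwards where weight has been gained. Anyone who cross-tabulated BMI by trimester of exposure would also see a gradient produced by timing alone.

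**Working it through.** The protocol gives no figure for BMI, weight gain or the number of exposures by trimester, so there is no plan figure to reproduce on this point. The precision table in section 9.5 concerns outcome risks and does not depend on BMI.

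**Inputs**
- From the protocol: time of weight measurement, cut-offs of 25 and 30, and the 85th to 90th percentile band (Appendix 5); exposure window (section 9.1.1).
- Assumed, because the documents are silent: height 1.55 to 1.65 m; gain of 0 to 2 kg for periconceptional or first-trimester exposure, 4 to 8 kg for second and 8 to 14 kg for third; pre-pregnancy BMI normally distributed with mean 23 to 25 and SD 4 to 5.

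**Shift in BMI.** Shift = gain / height². At 1.60 m, height² = 2.56.
- 5 kg: 5 / 2.56 = 1.95 kg/m2
- 8 kg: 8 / 2.56 = 3.13 kg/m2
- 12 kg: 12 / 2.56 = 4.69 kg/m2 (4.41 at 1.65 m, 4.99 at 1.55 m)

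A woman with a pre-pregnancy BMI of 22 and a 12 kg gain is recorded at 22 + 4.7 = 26.7 and moves from normal to overweight. Over the full assumed ranges the shift is 0 to 0.8 kg/m2 for periconceptional or first-trimester exposure, 1.5 to 3.3 for second and 2.9 to 5.8 for third. The fixed overweight band is 5 units wide.

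**Share classified at or above a cut-off.** Share ≥25 = 1 − Φ((25 − mean − shift) / SD), and likewise for 30. With mean 24, SD 4.5 and height 1.60 m:

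| Assumed gain | Shift (kg/m2) | Share ≥25 | Share ≥30 |
|---|---|---|---|
| 0 kg | 0 | 41.2% | 9.1% |
| 2 kg | 0.78 | 48.1% | 12.3% |
| 6 kg | 2.34 | 61.7% | 20.8% |
| 11 kg | 4.30 | 76.8% | 35.3% |

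With mean 23 and SD 4, the share ≥25 goes from 30.9% (0 kg) to 53.4% (6 kg) and 71.7% (11 kg). With mean 25 and SD 5, it goes from 50.0% to 68.0% and 80.5%.

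**Effect on the whole-cohort table.** This depends on how many women were exposed late, which is unknown. In the mean-24 example, each tenth of the cohort exposed at a 6 kg gain adds 0.10 × (61.7 − 41.2) = 2.1 percentage points to the overall share ≥25. Each tenth exposed at 11 kg adds 0.10 × (76.8 − 41.2) = 3.6 points.

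**Percentile band.** The 85th and 90th normal percentiles lie at z = 1.036 and 1.282, so the overweight band is 0.245 SD wide. At SD 4 to 5 that is 1.0 to 1.2 kg/m2, or 2.5 to 3.1 kg at 1.60 m. A modest gain can carry a woman across it.

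**Age check.** Take conception as LMP + 14 days. Vaccination at LMP − 30 days is 44 days earlier: −44 / 365.25 = −0.12 year. Vaccination at 42 weeks (LMP + 294 days) is 280 days later: 280 / 365.25 = 0.77 year.

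**The case against.** The row is labelled openly as BMI at vaccination, shares its time anchor with smoking, education and marital status, and sits in a table that also reports gestational age at exposure. A careful reader could interpret it. That is fair about the label, but a cohort-level percentage of overweight women cannot be corrected from a mean gestational age. Education and marital status also do not rise with gestation as weight does.

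The number of women affected is unknown. The only exposure-timing data in the protocol (section 7.1.3.2) place all pooled-trial exposures within about a month after LMP, where the shift is small. This stands as a limit on size. The same section warns that those results may not generalise to mass campaigns, so it does not remove the point.

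Several stronger readings are tempting, and the protocol does not support them:
- *The trimester groups will be reported as differing in BMI.* Sections 4 and 9.7.1 stratify outcomes by trimester. Section 9.7.2 describes the exposed population as a whole, and no baseline table by trimester is specified.
- *BMI biases the safety comparison.* BMI enters no adjusted or primary analysis; the external comparison is matched on age only.
- *The comparison with non-participants is distorted.* Section 9.8.1 seeks aggregate "information on the baseline characteristics and characteristics of prenatal care of non-participants" from the health databases. Sections 9.4 and 9.8.1 do not show that maternal weight or BMI is among those data.
- *Weight must be recalled years later.* The BMI rows do not state the source of weight, and medical records including the prenatal booklet are reviewed. Recall is possible but not required.
- *Age at conception is wrong by up to the gestational age at exposure.* The vaccination date only checks a questionnaire value; it does not derive it. This is unrelated to weight gain.

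**Conclusion.** The point holds as a cheap improvement to a descriptive result. Appendix 5 fixes a derivation under which pregnancy weight gain counts towards overweight and obesity for women vaccinated in the second or third trimester. For those women the inflation is about 2.0 to 4.7 kg/m2 at assumed gains of 5 to 12 kg and a height of 1.60 m; for periconceptional and first-trimester exposure it is at most about 0.8 kg/m2 under the assumed gains. How far this moves the whole-cohort percentages depends on the share of later exposures, which the protocol does not give. All weight-gain, height and BMI-distribution figures are assumptions.

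Sample size, the outcome risks and their intervals, and the comparison with background rates are unchanged. A BMI comparison by trimester would be misleading if someone made it, but the plan does not call for one. The age item is an inconsistency of wording worth less than 0.8 year.

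**What to change.** In Appendix 5, derive BMI for all women from pre-pregnancy weight or, failing that, from the first early-pregnancy weight in the prenatal booklet (for example at or before about 13 weeks), and record which source was used. If BMI at vaccination is kept, label it as gestational and do not sort it by the non-pregnant cut-offs.

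Reword the age row so that age at conception is verified from date of birth and LMP, or estimated conception date where LMP is missing.

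The cost is wording plus one weight item with its date. Appendix 6 already schedules review of the prenatal booklet, and the smoking and alcohol rows of Appendix 5 already ask about the month before pregnancy. The downside is that BMI will be missing for women with no early weight recorded, and the number missing should be shown. A self-reported pre-pregnancy weight is also open to recall error, which is a reason to record the source.
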